### 2.4.1 Completed Open-Label Study in PTSD Patients (IMPACT-1 Part A)

Part A of this study, completed in the UK, was an open-label evaluation of the safety, tolerability, and efficacy of methylone in adults with severe PTSD (CAPS-5  $\geq 35$ ; Jones 2023). Fourteen (14) participants were treated with open-label methylone once a week for 4 weeks (4 treatment sessions). During each treatment session, participants received an initial dose of 150 mg methylone followed by 100 mg of methylone 90 minutes later. Following the Treatment Period, participants entered a 6-week Follow-up Period and a final study visit at Week 10. The primary efficacy endpoint was the change from baseline on the CAPS-5 total severity score. At baseline, the mean CAPS-5 score was 47.8 points.

Treatment with methylone resulted in rapid, robust, and durable effects. Two days after the first dose, the mean change from baseline in CAPS-5 total severity score was -8.4 points. Methylone provided robust improvements in CAPS-5, with the mean change from baseline of -23.3 points two days after the 2nd dose. Six weeks after the last dose, the results were durable with a mean change from baseline in CAPS-5 of -36.2 points. Remission, defined as a CAPS-5 total score of  $\leq 11$ , was achieved by the majority of participants (61.5%) at the end of study.

Methylone was well tolerated with no drug-related or treatment-emergent serious adverse events to date. The most commonly occurring treatment-emergent adverse event (TEAE) was headache (43%), followed by decreased appetite (29%), non-cardiac chest pain (21%), and fatigue (21%). One unrelated serious adverse event of 'victim of assault' occurred after a participant was off study drug for 20 days.

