### **9.2 Sample Size Determination**

No formal sample size calculation was performed for Part A of the study. The sample size of approximately 15 participants in the open-label study is based on medical and clinical considerations.

Sample size calculations for Part B were performed using PASS 2022 to determine the sample size required to detect a significant difference between CAPS-5 scores in the methylone and placebo groups (the efficacy endpoint). A previous phase 3 trial investigating the effects of MDMA versus placebo on CAPS-5 scores found a placebo-corrected treatment effect at the end of treatment of 11 points and a pooled standard deviation (SD) of 12 (Mitchell 2021). Assuming a treatment effect of 11 points and a pooled SD of 12 in this trial, with a sample size of 20 or 27 evaluable participants in each treatment group, the trial should provide 80% or 90% power, respectively, to detect a treatment difference at two-sided significance level of 0.05. Assuming a dropout rate of 15%, a target sample size of 46 (23 per treatment group) or 64 (32 per treatment group) will provide 80% or 90% power, respectively.

A DSMB will monitor the clinical data.

An N of 20 or more in each treatment group should also provide useful safety and tolerability data, without exposing too many individuals.

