## 4 SAMPLE SIZE DETERMINATION

Sample size calculations for Part B were performed using PASS 2022 to determine the sample size required to detect a significant difference between CAPS-5 scores in the methylone and placebo groups (the efficacy endpoint). A previous phase 3 trial investigating the effects of MDMA versus placebo on CAPS-5 scores found a placebo-corrected treatment effect at the end of treatment of 11 points and a pooled standard deviation (SD) of 12 (Mitchell 2021). Assuming a treatment effect of 11 points and a pooled SD of 12 in this trial, with a sample size of 20 or 27 evaluable participants in each treatment group, the trial should provide 80% or 90% power, respectively. Assuming a dropout rate of 15%, a target sample size of 46 (23 per treatment group) or 64 (32 per treatment group) will provide 80% or 90% power, respectively.

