### **8.1.6 Tests**

All tests will be based on one-sided significant level of 0.05. In addition to the tests, two-sided 90% confidence intervals will be reported.

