### 8.3.1 Statistical Methods

#### 8.3.1.1 Analyses for Continuous Efficacy End Points

A Mixed Model for Repeated Measures (MMRM) will be fitted for select efficacy endpoints to analyze the difference between treatments. The model will include treatment, visit, and treatment by visit interaction as fixed effects, where visit is the repeated effect. The endpoints baseline value (if applicable) and sex will be included as covariates.

The covariance structure will be modeled using an “unstructured” (UN). Other covariance structures may be considered if the UN model does not converge, such as AR(1), and CS. The visit-by-treatment interaction allows for potential differences in the treatment effect at different time points. Pairwise contrasts will be constructed to compare the methylene group to the placebo group at each visit specifically.

Besides, summary statistics will be provided for the actual values and for the change from baseline.

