## 11.3 Appendix 3 MMRM and CMH SAS Sample Code

This MMRM approach can be implemented in SAS by a code similar to the following:

```
proc mixed data = adef method=REML;
  class Subjid trtpn avisitn;
  model Chg=trtpn avisitn trtpn*avisitn base sex/ddfm=kr; /* The baseline value will be
  included (if applicable) as a covariate.*/
  repeated avisitn/ subject = Subjid type=un;
  lsmeans trtpn trtpn*avisitn/diff cl;
  ods output Tests3=b1 LSMMeans=b2 Diffs=b3;
run;
```

This CMH approach can be implemented in SAS by a code similar to the following:

```
Proc freq data=adef;
  Tables trtpn*outcome/cmh riskdiff;
  Weight count;
Run;
```

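### If the unstructured MMRM does not converge, the only named fallbacks force one variance on all eight CAPS-5 visits, so the Week 10 standard error could be wrong in either direction

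*SAP*

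**What the plan says.** SAP 8.3.1.1 specifies an MMRM with treatment, visit and their interaction, adjusted for baseline and sex, with a UN covariance. Its fallback is one sentence: "Other covariance structures may be considered if the UN model does not converge, such as AR(1), and CS". It gives no order of preference, no structure with visit-specific variances and no robust standard error.

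The sample code in SAP 11.3 has "model Chg=trtpn avisitn trtpn*avisitn base sex/ddfm=kr" and "repeated avisitn/ subject = Subjid type=un". These are model-based standard errors with Kenward-Roger degrees of freedom, and no empirical (sandwich) option is set.

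The Schedule of Assessments (Protocol 1.3) places the past-week CAPS-5 at eight post-baseline visits: Days 3, 10, 17, 24, 29, 36, 43 and 64. Protocol 9.5.2 sets the primary comparison at Week 10, which is the last of these. On testing, SAP 8.1.6 states: "All tests will be based on one-sided significant level of 0.05". It also calls for two-sided 90% confidence intervals.

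**The concern.** AR(1) and CS each estimate one variance for all eight visits. Because the model has a treatment-by-visit term, the Week 10 contrast is close to a plain difference in Week 10 means, and its standard error should reflect the Week 10 variance. Under either fallback it reflects an average over all visits. Kenward-Roger allows for uncertainty in the covariance parameters of the chosen structure; it does not correct a wrong structure.

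A rise in spread over time is plausible. On Part A, Protocol 2.4.1 reports: "Two days after the first dose, the mean change from baseline in CAPS-5 total severity score was -8.4 points". By Week 10 the mean change was -36.2. In addition, the Day 3 past-week interview looks back over days that are mostly before the first dose, so its scores should track baseline closely. Day 64 scores need not, and the variance left after baseline adjustment could therefore grow even with no treatment effect. If it does, the primary p-value is too small and the 90% interval too narrow. SAP 8.1.5 says the results will be used to design and power later trials.

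The permissive wording also leaves the choice of structure until after the data have been seen.

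**Working it through.** **Inputs.** Planning effect and SD (SAP 4): "Assuming a treatment effect of 11 points and a pooled SD of 12 in this trial". This is one SD, with no SD or correlation by visit. Evaluable participants: 20 or 27 per arm. Dropout: 15%. Test level: one-sided 0.05 (SAP 8.1.6).

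**The plan's own figure.** The protocol's calculation is "to detect a treatment difference at two-sided significance level of 0.05". A two-sample t-test with difference 11 and SD 12 gives 80.6% power at 20 per arm and 91.1% at 27, so 20 and 27 reproduce. For dropout, 27/0.85 = 31.8, which gives 32 per arm and 64 in total, as stated. 20/0.85 = 23.5 gives 24 per arm, or 48 against the stated 46; this does not affect the present point. The documents state no error rate for the fallback.

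**Number of UN parameters.** 8 × 9 / 2 = 36.

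**Size under a one-variance structure, complete data.** Let k = (root mean square of the eight visit SDs) / (Week 10 SD). The reported standard error is k times the true one, so the one-sided size is P(Z > 1.645k) and the 90% interval covers 1 − 2 × size.

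Example, SD rising evenly by visit number from 8 to 12: mean variance = 64 + 2×8×4×0.5 + 16×0.357 = 101.7. The root is 10.09, k = 10.09/12 = 0.840, and P(Z > 1.382) = 8.3%.

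| Assumed SD path to 12 at Week 10 | from 10 | from 8 | from 6 |
|---|---|---|---|
| Even rise by visit number | 6.5% | 8.3% | 10.3% |
| (90% CI coverage for that row) | 87% | 83% | 79% |
| Front-loaded as the Part A means, then linear to Day 64 | 6.1% | 7.3% | 8.7% |
| Straight line in time, complete by Day 24 | 5.7% | 6.4% | 7.1% |
| Front-loaded, complete by Day 24 | 5.6% | 6.2% | 6.7% |

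The front-loaded shape puts (23.3 − 8.4)/(36.2 − 8.4) = 54% of the rise by Day 10.

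A constant SD gives 5.0%. For an SD that falls, a ratio of first-visit to Week 10 SD of 1.1 to 1.5 gives 4.1% to 1.6% (linear in time) or 4.6% to 3.0% (plateau at Day 24). Over ratios from 0.5 to 1.5, linear in time, the size runs from about 12% to 2%.

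**Check with dropout.** REML fits of the SAP mean model were simulated with 32 per arm, the real visit days, 15% monotone dropout and 1,200 to 2,000 runs (Monte Carlo error about 0.4 to 0.5 points; a t critical value with 100 df stood in for Kenward-Roger). At SD ratio 0.7, linear, CS gave 8.1–8.4% and AR(1) 7.6–7.9%. At ratio 1.3, linear, CS gave 3.5% and AR(1) 2.8%. With equal SDs, CS gave 4.9–6.1% and AR(1) 5.1–5.5%.

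**Visit spacing.** The gaps are 7, 7, 7, 5, 7, 7 and 21 days, and AR(1) on visit number treats them as equal. The equal-SD result for AR(1) shows that this alone adds little.

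**Does a heterogeneous structure suffice?** In 2,000 complete-data trials (32 per arm, SD 8 to 12, an assumed decaying correlation), CS and AR(1) gave about 7.6% and UN 4.4%. ARH(1) and CSH with model-based errors gave about 2.8%. A large-sample calculation with correlation 0.35 + 0.65·exp(−days/20) agrees in direction: 2.8% for ARH(1) and 3.5% for CSH. When the true correlation is compound symmetric, both return 5.0%.

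**The case against.** **The trigger is not shown to be likely.** UN is the plan, and nothing in the documents says it will fail. Thirty-six covariance parameters look heavy against 54 to 64 participants, but those participants supply roughly 430 to 510 CAPS-5 values. In 400 simulated trials (46 or 64 participants, 15% or 30% dropout), a REML fit of UN by an EM algorithm reached a positive-definite solution every time. PROC MIXED uses a different algorithm, so failure is not excluded. Sample size alone does not make it probable.

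**The direction is not established.** A reader might infer that the fallback makes the Week 10 test anti-conservative, at 6.5% to 10%. The documents do not support that. Part A reports means, not SDs, and a growing mean is not a growing variance. In the same section, 61.5% of participants ended at CAPS-5 of 11 or less on a scale bounded at zero, so a floor could compress late scores. In reply, type I error concerns two arms with no difference, and neither the Part A trajectory nor its remission rate need apply there. The argument about decaying correlation with baseline does favour a rise, but its size rests on assumed correlations: linear declines of 0.8 to 0.4, 0.7 to 0.5 and 0.6 to 0.5 give 8.5%, 6.8% and 5.8%.

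**The wording is permissive.** The two structures are offered as examples, so a heterogeneous one is already allowed, and SAP 8.1.5 describes the trial as not confirmatory.

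The first two objections stand and limit the point. The third reduces its weight but leaves the choice open until the data are seen.

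**Conclusion.** The point holds as a conditional one. The fallback is unordered, names only common-variance structures and carries model-based standard errors. If UN fails and one of them is used, the Week 10 standard error depends on a constant-variance assumption that the documents give no way to check, and the error may go either way.

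The size rests on an assumed path of SD by visit: about 6.5% to 10% for an even rise by visit to 12 from 10 down to 6; about 5.6% to 7.1% if the rise is complete by Day 24; about 5% if constant; below 5% (conservative) if the SD falls. Unequal visit spacing is a minor contributor, and the probability of non-convergence is unknown. A flat statement that the primary test is inflated would go beyond the documents. This is an inexpensive improvement to consider, not a flaw in the main analysis.

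**What to change.** In SAP 8.3.1.1, replace the fallback sentence with a fixed rule: use the first structure to converge, in the order UN, heterogeneous Toeplitz (TOEPH), ARH(1), CSH. For any structure other than UN, report small-sample-corrected empirical (sandwich) standard errors for the Week 10 contrast, and name a compatible degrees-of-freedom method in place of ddfm=kr. Add the matching code to SAP 11.3.

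The sandwich error is the essential part, because ARH(1) and CSH with model-based errors can also miss the nominal level. With complete data it is essentially the UN standard error for this contrast, which gave 4.4% in the simulation above. TOEPH and the corrected sandwich under dropout were not simulated. A sandwich error repairs the standard error, not any bias in the estimate if dropout depends on earlier scores and the covariance is wrong, which is a reason to keep the richer structures first.

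Cost: a few lines of SAP text and code, a few more covariance parameters than AR(1) or CS, and slightly different code for the fallback. The main UN analysis does not change.

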#### 8.3.1.2 Analyses for Categorical Efficacy End Points

Frequency tables and the Cochran–Mantel–Haenszel (CMH) test will be applied to the actual value of each visit. The descriptive statistics (n and percentage) for the treatment arms, and difference between treatment arms as well as the two-sided confidence interval of the treatment difference will be presented. The confidence interval will be constructed based on normal approximation.

See [Appendix 3 MMRM and CMH SAS Sample Code](#).

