### **8.1.7 Covariates**

For the analysis of select efficacy endpoints, the baseline value will be included (if applicable) as a covariate. Sex will also be used as a covariate.

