#### 8.3.2.2 Secondary Endpoint

##### 8.3.2.2.1 CAPS-5

The CAPS-5 total severity score (absolute, change from baseline) will also be summarized by visit.

Summary percentage of participants by visit having

- Treatment response, defined as:
  - $\geq 10$  point reduction on the CAPS-5 from baseline
  - $\geq 30\%$  improvement from baseline on CAPS-5
  - $\geq 50\%$  improvement from baseline on CAPS-5
- Remission, defined as:
  - A score of  $\leq 11$  on the CAPS-5

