#### **8.3.2.2.10 PGI-C**

The number and percentage of each level the PGI-C will be summarized.

Improved items include: “Very much improved”, “Much improved”, “Slightly improved”.

The number and percentage of improved rate on the PGI-C will be summarized and compared between treatment groups using CMH test.

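### CAPS-5 remission is analysed without the baseline CAPS-5 and sex adjustment used in the MMRM; the planned test is valid but may be less precise than it could be

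*SAP*

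**What the plan says.** SAP 8.3.1.2 sets one rule for all categorical efficacy endpoints: the Cochran–Mantel–Haenszel (CMH) "test will be applied to the actual value of each visit". It names no stratification factor. For the treatment difference it adds: "The confidence interval will be constructed based on normal approximation". The sample code in SAP Appendix 3 is "Tables trtpn*outcome/cmh riskdiff", a two-way table.

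The continuous endpoints are treated differently. SAP 8.3.1.1 states "The endpoints baseline value (if applicable) and sex will be included as covariates", and the MMRM code carries both terms: "model Chg=trtpn avisitn trtpn*avisitn base sex/ddfm=kr". SAP 8.1.7 gives the general rule that baseline is a covariate for selected efficacy endpoints, and adds "Sex will also be used as a covariate". It does not say whether the binary endpoints are among those selected.

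In its own subsection (SAP 8.3.2.2.1), CAPS-5 remission is listed only under "Summary percentage of participants by visit having", with no test named. For PGI-C the test is explicit: "The number and percentage of improved rate on the PGI-C will be summarized and compared between treatment groups using CMH test". CGI-I has matching text. A test of remission therefore rests on the general rule in 8.3.1.2.

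Protocol 9.1 randomises 1:1 in blocks of 4 and states no stratification factor.

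**The concern.** With a single stratum, the CMH statistic is the ordinary 2×2 chi-square apart from a factor (N−1)/N, and the risk difference is the raw one. Nothing known about the participant at entry is used.

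For remission that may matter. The threshold is fixed at 11, while Protocol 6.1 admits any baseline score of 28 or more. A participant who enters at 30 needs a fall of 19 points; one who enters at 60 needs 49. If the fall does not grow in step with the entry score, baseline predicts remission, and leaving it out costs precision. Because neither the randomisation nor this analysis uses baseline, a chance difference in entry severity between arms of about 27 to 32 also passes into the remission difference.

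Part A reported 61.5% remission (Protocol 2.4.1), and the SAP says the results will help to design and power later trials (8.1.5). The precision of this estimate is therefore of practical interest.

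**Working it through.** **The plan's own figures.** Neither document states power or precision for remission. The design figure reproduces: with 11 points, SD 12 and two-sided 0.05, t-test power is 80.6% at 20 per arm and 91.1% at 27 per arm. Dropout inflation gives 27/0.85 = 31.8, so 32 per arm and 64 in total. I therefore use 27 and 32 per arm.

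**Inputs.** From the documents: baseline mean 47.8 and Week 10 change −36.2 (Part A, Protocol 2.4.1), entry floor 28, effect 11, SD 12, one-sided 5% (SAP 8.1.6). Assumed: baseline SD 8, placebo change −20 or −25, and sex not prognostic. The baseline-to-Week-10 correlation ρ is unknown and is varied.

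**Step 1: linking slope and correlation.** Let s be the slope of change on baseline. With baseline SD 8 and change SD 12,

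ρ = 8(1+s) / √[(8(1+s))² + 144 − 64s²].

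- s = 0: 8/√208 = 0.55
- s = −0.3: 5.6/√169.6 = 0.43
- s = −0.5: 4/√144 = 0.33
- s = −0.75: 2/√112 = 0.19

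**Step 2: precision, varying ρ.** 2,500 simulated trials per scenario compared the unstratified CMH with a standardised logistic risk difference adjusted for baseline and sex. The variance ratio is unadjusted over adjusted; its range covers 27 and 32 per arm and both placebo changes. Power is for 27 per arm with about 16% against 47% remission.

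| ρ | Variance ratio | Power, unadjusted | Power, adjusted |
|---|---|---|---|
| 0 | 0.95–0.98 | 82.6% | 82.0% |
| 0.2 | 0.96–0.99 | 82.7% | 82.6% |
| 0.4 | 1.02–1.05 | 82.6% | 84.5% |
| 0.6 | 1.10–1.23 | 81.7% | 88.7% |

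**Step 3: precision, varying s.** This used 3,000 trials, 27 per arm, and mean changes −36 and −25. Adjusting for baseline alone, the unadjusted variance was 19%, 11% and 5% larger at ρ = 0.55, 0.43 and 0.33. With a non-prognostic sex term added, repeat runs gave 16–17%, 5–6% and 3–4%. At ρ = 0.19 the ratio was 0.96, so adjustment cost a little.

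**Step 4: chance imbalance.** The SD of the arm difference in mean baseline is 8√(2/27) = 2.2 points, or about 2.1 once the floor at 28 is applied. One point of imbalance moves the raw remission difference by about (1+s) times the mean over arms of φ(z)/SD₁₀. Here SD₁₀ is the Week 10 SD, the denominator in Step 1, and z = (11 − Week 10 mean)/SD₁₀. The Week 10 means are 47.8 − 36 = 11.8 and 47.8 − 25 = 22.8.

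- s = 0: (0.398 + 0.285)/2/14.42 = 2.4 percentage points
- s = −0.3: 0.7 × (0.398 + 0.265)/2/13.02 = 1.8
- s = −0.5: 0.5 × (0.398 + 0.246)/2/12 = 1.3

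Simulation gave 2.4, 1.7 and 1.4, against 0.2 or less for the adjusted estimate. A one-SD imbalance therefore shifts the raw difference by about 2.1 × 1.4 = 3 to 2.1 × 2.4 = 5 points. A further run with a Firth-penalised fit gave 1–2 points per point of imbalance unadjusted and 0–0.3 adjusted. Its power ran from 2 points lower to 3 points higher with adjustment.

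**Step 5: would strata in the CMH be enough?** No. Relative to the unstratified analysis, stratifying by sex alone gave a variance of 1.01–1.03. Sex by median baseline gave 0.98–1.03 at ρ = 0.4.

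**Step 6: null behaviour at 27 per arm.** Rejection was 5.6–5.8% for the CMH and 6.1–6.5% for the adjusted analysis. The nominal level is 5%, with Monte Carlo SE √(0.05 × 0.95/2500) = 0.4 points.

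**The case against.** The strongest reply is that the loss is conditional on something the documents do not report. If improvement is proportional to entry severity, the Part A means imply a slope near −36.2/47.8 = −0.76. By Step 1 that puts ρ at about 0.19, where adjustment gains nothing. At s = −0.75 simulated power was 89.2% unadjusted against 89.3% adjusted; at s = −1 it was 94.7% against 94.2%. This stands, and it rules out saying that the plan does lose precision.

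Randomisation protects the test. Chance imbalance is already covered by the type I error rate and the confidence interval. This also stands: Step 4 concerns how far one trial's estimate can move, not bias. The slightly raised null rejection in Step 6 means part of the apparent power gain may be anti-conservatism, which is why a small-sample variance belongs in the fix.

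A reader might infer that every binary endpoint is affected. The numbers do not support that. The 50% response gains 0–1 point of power, and the 10-point and 30% definitions gain nothing material. PGI-C and CGI-I have no baseline of their own scale in the protocol's schedule of assessments.

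A reader might also infer that SAP 8.1.7 already requires adjustment, so that the CMH contradicts it. The baseline rule there covers only selected endpoints. The binary ones are not named, so this is a difference in treatment rather than a contradiction.

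The objection does not remove the narrower point. For remission, a covariate already collected and used elsewhere could help and costs little.

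**Conclusion.** The point holds for CAPS-5 remission only, as a cheap improvement and not as an error. The unstratified CMH is a valid test, and nothing here shows bias or an inflated type I error in the plan.

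The unadjusted variance is roughly 15–20% larger at ρ about 0.55–0.6 (individual scenarios span 10–23%), a few percent larger near 0.4, and no larger at 0.2 or below. There, adjustment costs about 1–5% in variance. Even in the favourable case the binary analysis recovers only part of what the MMRM can: the large-sample residual variance factor for the continuous score is 1 − ρ² = 0.84 at ρ = 0.4 and 0.64 at 0.6.

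These sizes rest on the assumed baseline SD of 8, the assumed placebo change, and sex not being prognostic. The trial is declared non-confirmatory (SAP 8.1.5) and the primary analysis already adjusts, which limits the consequence.

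**What to change.** In SAP 8.3.1.2, 8.3.2.2.1 and Appendix 3, for CAPS-5 remission only:

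- State whether remission is tested or only summarised.
- Prespecify at Week 10 a logistic regression on treatment, baseline CAPS-5 (the same value as in the MMRM) and sex. Report the standardised (marginal) risk difference with a two-sided 90% confidence interval based on a small-sample variance.
- Fix one sparsity rule in advance. For example, report only the unadjusted result at any visit with fewer than a stated number of remitters. A choice among several fallbacks after seeing the data would be worse than the present plan.
- Keep the raw percentages and the unstratified CMH as supportive.

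The response rates, PGI-C and CGI-I can stay as planned.

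The cost is a few sentences, a little more code, a fallback at early visits with few remitters, and a slight loss of precision if baseline proves not to be prognostic. Fixing the choice before unblinding also prevents a later selection between adjusted and unadjusted remission results.

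### The normal-approximation interval for response and remission differences has no fallback for sparse cells and can print as [0, 0] when neither arm has an event; a score-type interval would cure this (minor).

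*SAP*

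**What the plan says.** SAP 8.3.1.2 covers all categorical efficacy endpoints. The CMH "test will be applied to the actual value of each visit", per-arm counts and percentages are shown, and a "two-sided confidence interval of the treatment difference will be presented". On method it says "The confidence interval will be constructed based on normal approximation". It gives no confidence level. The level comes from SAP 8.1.6: "In addition to the tests, two-sided 90% confidence intervals will be reported".

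The sample code in SAP Appendix 3 reads "Tables trtpn*outcome/cmh riskdiff". It has no option for a score, Newcombe or exact interval, no continuity correction and no alpha setting.

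The endpoints concerned include three CAPS-5 response definitions and CAPS-5 remission (a score of 11 or less), reported by visit under SAP 8.3.2.2.1. SAP 4 plans 27 evaluable participants per arm for 90% power, or 32 randomized per arm after 15% dropout. SAP 7.1 uses available data without imputation, so the number per visit falls as participants leave.

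**The concern.** The Wald interval estimates its standard error from the observed proportions. When those are near 0 or 1 the estimated standard error is near zero, and it is exactly zero when each arm is at 0% or 100%. A visit with no remitter in either arm would then be reported as a difference of 0 with limits 0 and 0, which reads as if the difference were known exactly.

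This could happen in the trial. Protocol 2.4.1 reports for Part A a mean baseline CAPS-5 of 47.8 and a mean change of -8.4 two days after the first open-label dose. The implied mean of 39.4 is 28.4 points above the remission threshold. Protocol 6.1 requires at least 28 at Baseline, so even the mildest eligible participant must fall by 28 - 11 = 17 points. Few or no remitters at Day 3 is a fair inference, but the documents give no early remission rate.

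At stake is how the precision of secondary results is reported. SAP 8.1.5 says the findings will serve to design and power later trials, and SAP 9 says the analyses may go into submissions or manuscripts.

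**Working it through.** **Inputs.** Per-arm n of 27 and 32 (SAP 4); two-sided 90% level, z = 1.645 (SAP 8.1.6); active-arm remission of 61.5% at end of study in Part A (Protocol 2.4.1). All other true rates are assumptions, shown as a range.

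**The plan's own sample size.** For a difference of 11, SD 12 and a two-sided 0.05 t-test, power is 80.6% at 20 per arm, 89.99% at 26 and 91.1% at 27. So 27 is the smallest n reaching 90%. Then 27 / 0.85 = 31.8, or 32 randomized. The planned 27 and 32 reproduce. The documents give no coverage figure or planning rate for the categorical endpoints.

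**Formulas.** Wald: (p1 - p2) ± 1.645 × √[p1(1 - p1)/n + p2(1 - p2)/n]. Newcombe combines the Wilson limits of each arm. Coverage and mean width come from exact enumeration of every pair of binomial outcomes.

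**No events in either arm.** Wald gives 0 ± 0. The Wilson upper limit for 0/n is z²/(n + z²): 2.706/29.706 = 0.091 at n = 27 and 2.706/34.706 = 0.078 at n = 32. Newcombe therefore gives [-0.091, 0.091] and [-0.078, 0.078]. Miettinen-Nurminen gives [-0.093, 0.093] and [-0.079, 0.079].

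**Probability of that outcome** with the same true rate p in both arms, (1 - p)^(2n):

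| p | n = 27 | n = 32 |
|---|---|---|
| 1% | 58% | 53% |
| 2% | 34% | 27% |
| 5% | 6.3% | 3.8% |

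**Why coverage drops at 5% versus 2%.** The true difference is 0.03. If the 5% arm shows no event, the largest possible Wald upper limit is 0.023 at n = 27 (0.019 at n = 32), so the interval misses. That has probability 0.95^27 = 25.0% (0.95^32 = 19.4%). Adding the other misses gives coverage of 72.3% and 79.3%.

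**Range of assumed rates, nominal 90%:**

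| True rates | Wald coverage, n = 27 / 32 | Newcombe coverage, n = 27 / 32 | Mean width at n = 27, Wald / Newcombe |
|---|---|---|---|
| 2% vs 2% | 98.1% / 97.3% | 99.8% / 99.6% | 0.098 / 0.209 |
| 5% vs 2% | 72.3% / 79.3% | 96.8% / 96.2% | 0.144 / 0.227 |
| 20% vs 5% | 87.0% / 87.5% | 92.7% / 91.8% | 0.280 / 0.303 |
| 50% vs 20% | 89.2% / 89.1% | 89.3% / 89.6% | 0.397 / 0.386 |
| 60% vs 10% | 86.7% / 87.6% | 90.1% / 90.2% | 0.356 / 0.353 |
| 61.5% vs 10% | 89.4% / 89.8% | 89.7% / 90.5% | 0.354 / 0.351 |
| 61.5% vs 20% | 88.5% / 88.6% | 88.4% / 90.6% | 0.390 / 0.379 |

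Over a grid of rates from 10% to 90%, Wald coverage averages 88.6%, with minimum 86.5% (n = 27) or 85.5% (n = 32). Over 5% to 95% it averages 88.5%, with minimum 74.2% or 82.2%. On the wider grid Miettinen-Nurminen averages 90.0% or 90.1%, with minimum 88.4% or 88.5%.

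**The case against.** The strongest reply is that a reader might infer from this that the response and remission intervals are too narrow in general. The documents and the arithmetic do not support that. At 50% vs 20%, 60% vs 10% and both 61.5% comparisons, the mean Wald width equals or slightly exceeds the Newcombe width. Coverage at the only active-arm remission rate in the documents, against assumed placebo rates of 10% to 20%, is 88.5% to 89.8%. The 86.7% at 60% vs 10% is partly lattice oscillation: at 58% vs 10% it is 89.7%. This part of the reply stands.

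It is also fair that the [0, 0] example is not under-coverage. With equal rates of 2% the true difference is zero, so [0, 0] contains it and coverage is above nominal. The complaint there is about an interval that conveys false precision. Collapse also needs both arms at a boundary; a low placebo rate alone does not produce it.

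A 3/27 versus 0/27 split might suggest that Wald finds differences where better methods do not: Wald gives [0.012, 0.211] and Newcombe [-0.001, 0.248]. But Miettinen-Nurminen gives [0.013, 0.249] and also excludes zero. Only the understated upper limit is common to both comparisons.

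Finally, little hangs on these intervals. The endpoints are secondary, the SAP calls the study non-confirmatory, counts are printed beside each interval, and near-zero early remission is an inference from 14 open-label participants with no SD given. A 10-point response need not be rare when the mean change is already -8.4. All of this limits the severity. It does not remove the missing rule for sparse visits.

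**Conclusion.** The point holds in a limited form. Followed as written, the SAP would print a zero-width interval at any visit with no events in both arms, and its interval is badly short of nominal coverage when rates are low and unequal (72% with 27 per arm, 79% with 32, at 5% versus 2%). Early visits, before most dropout, would probably be nearer 32 per arm, so the milder figure is the more relevant one there. Elsewhere the shortfall is usually 1 to 2 points and of little practical weight.

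It would be wrong to conclude that the categorical tests or the primary result are compromised: the CMH test does not use the Wald standard error, and the MMRM is separate.

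The verdict rests on reading the method as uncorrected Wald, which the bare code supports (a continuity correction would prevent zero width, but none is mentioned), and on assumed true rates. Severity is minor.

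**What to change.** In SAP 8.3.1.2, replace the normal-approximation sentence with one stating that intervals for risk differences are score-type, naming either Miettinen-Nurminen or Newcombe in advance, at the two-sided 90% level of SAP 8.1.6. In Appendix 3, use `riskdiff(cl=(mn))` or `riskdiff(cl=(newcombe))` with `alpha=0.10`, so that the code matches the text on both method and level.

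The cost is one sentence and one line of code. Intervals become wider where cells are sparse (mean width at 5% vs 2%, n = 27: 0.227 with Newcombe against 0.144), and Newcombe is conservative there, covering about 97%. At mid-range rates the intervals barely change and may be marginally narrower. No change to design, data collection or the tests is needed.
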